Complexity and extent of liver surgery, patient selection and both centre and surgeon experience are all cited factors which may influence outcomes following major liver surgery. A large, single-centre analysis of outcomes following liver surgery found that the number of hepatic segments resected and operative blood loss were the only two predictors of both perioperative morbidity and mortality.⁵ The authors suggest that whilst 'complex liver resections' defined as liver surgery with one or more major extrahepatic procedure, were associated with a higher mortality in conjunction with major hepatectomies, complexity had no impact on mortality when performed with minor hepatectomies, thus highlighting the importance of future liver remnant percentage (FLR) which has since been repeatedly demonstrated.^{8,9} Induction of regeneration prior to resection using portal vein embolization, portal vein ligation or Associating Liver Partition and Portal vein ligation for Staged hepatectomy (ALPPS) are evolving strategies to mitigate the adverse outcomes associated with a major liver surgery. Such staged approaches to major liver resections are associated with a perioperative mortality of over 5% even in the most experienced centers¹²⁻¹⁴ with the ALPPS procedure reported to have a mortality of 12% in voluntary registry studies.¹⁵ Whether such strategies improve the safety of major liver surgery, or instead allow a more aggressive approach to resection of lesions previously deemed unresectable is contentious.

At the extreme end of complexity are ex-situ and ante-situ resections. The largest series of standardized in-situ hypothermic perfusion for patients with tumours involving the vena cava and the hepato-caval junction identified an overall mortality rate of 20%.¹⁸

An open debate and ultimately consensus amongst the HPB surgical community is required to address the delicate balance between improving mortality of liver surgery whilst developing approaches to treat the most challenging lesions. To inform this debate a robust prospective audit examining the current international experience and outcomes is required. Existing registry studies are based on national (French Liver surgery registry, Scandinavian liver surgery registry LiverMET Survey SweLiv²¹, Italian laparoscopic liver surgery registry²²) or

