Data are “surgeon-based”, not “centre-based”. Surgeons participating in LiverGroup.org are only responsible for their own data. The data will indicate in an anonymized fashion that surgeons belong to a specific centre. Data will be entered using a personalized login assigned to surgeons, their assistants and in some centres, study nurses. The complete dataset of the electronic Case Report Form (CRF) are available at <https://livergroup.org/?q=instructions>.

Each CRF has a unique identifier. A participant may enter data for a colleague or partner under their login, as long as authorization has been granted by the user. If centres are not willing to disclose their identity to the management committee when asked to do so for the purpose of an audit, they are free to have their data excluded from the analysis. Such exclusion will be reported in the final report for transparency while assuring that the data are under control of the individual centre until the final analysis and audit is performed.

Data collection

Data will be entered directly onto the electronic CRF available at <https://livergroup.org/?q=CRF> which includes the unique identifier. Collaborators keep a paper key list connecting the unique database identifier with the patient name in a safe place locked away under their control and their responsibility. If the list gets lost and audit is impossible, the surgeons’ data will be excluded from the final analysis and reported in the final report. The LiverGroup.org management committee cannot identify an individual patient or surgeon or centre without contacting the local PI who entered the data and is in possession of the key to the data.

Data collection methods

The Management Committee currently consists of clinicians who will review data entered, monitor progress and maintain the platform and send reminders to the participants regarding completion of data or questions regarding clarifications. Any collaborator is welcome to join the Management Committee. This practice is introduced to avoid the proprietary use of the collected data by a few “founding members” or “coordinators” or members of an appointed “scientific committee”.

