To avoid *selective reporting*, all consecutive patients undergoing liver resections by one individual surgeon over three months are included. In some patients the operation may not run the expected course, be aborted or changed in scope. Intraoperative findings may change the operative plan. These patients should also be recorded in the registry following the principle of intent-to treat to avoid incomplete reporting.

An audit of the consecutively, intent-to-treat, completeness of data entered will be performed by random selection of the contributing surgeons. A member of LiverGroup.org will be assigned to audit one fellow surgeon of LiverGroup.org to perform a validation of the number of and date of deaths. This randomly assigned peer-review by participating centres is entirely novel and has not been routinely performed in similar snapshot studies, to the best of our knowledge. In detail, e.g. a surgeon/monitor from site A will monitor site B while a surgeon/monitor from site B will monitor site C. The monitors themselves may want to carry the costs for the monitoring, but in case that is not possible, LiverGroup.org may help to provide funding from third parties.

As for the quality of the data collected, the electronic CRF is specially designed to force data entry for the important variables (e.g. comorbidities, procedure type, morbidity, mortality, etc.), has minimum and maximum allowed values to avoid typing errors for continuous variables, all categorical data are captured in the form of selection lists and there is a description for important variables within the CRF. Additionally, there are calculators available at LiverGroup.org (e.g. sFLR and conversion of lab values) to ensure uniform data capture. Furthermore, information regarding the Brisbane, Clavien-Dindo, FABIB, BCLC Staging, and Bismuth-Corlette classifications is also available at LiverGroup.org.

All participants will have the opportunity to read study documents available at LiverGroup.org including instructions as well as contact the Management Committee in case they have questions directly through the platform.

Data management

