LiverGroup.org is a Clinical Trial Management System (CTMS) built on Drupal 7 that will act as the backbone of our study, by supporting administration, collaboration, communication and information sharing needs among members from several centres worldwide. Anonymised patient data will be stored in two separate secured sites with access given only to the relevant users. There will be regular backups. Furthermore, the CTMS is secured with a Hypertext Transfer Protocol Secure (HTTPS) in combination with a SSL/TLS protocol and an encrypted SQL database.²⁴

The study sponsors, Royal Free Hospital London and University of Zaragoza, will act as the custodians of the data. The steering and management committees together will decide after the publication of the main report about requests regarding secondary analysis and will consider all such requests based on quality and the validity of the proposed project and decide by majority decision.

Statistical methods

The primary endpoint of the analysis will be the 90-day mortality; secondary endpoints will be liver failure by Clavien-Dindo score,²³ the FABIB classification, complications, length of stay and incidence of re-hospitalisation. Descriptive statistics will be performed. Continuous variables will be compared with the Student t test, the Mann-Whitney U test and the Kruskal-Wallis H test or one-way ANOVA as appropriate. Differences among proportions derived from categorical data will be compared using the Fisher test and the Pearson chi-square. Univariate analysis will be performed to test factors associated with post-operative complications and 90-day mortality. Multivariable regression models will be used to identify factors independently associated with these outcomes and to adjust for differences in confounders. Results of the multivariable analyses will be reported as adjusted odds ratios (OR) with 95% confidence intervals. ROC curves and the Youden's index will be used to identify ideal cut-off points for continuous variables. All p values will be 2-sided and considered statistically significant if $p < 0.05$. The statistical analysis will be performed using R version 3.3.2 (R Core Team, GNU GPL v2 License), R Studio version 1.0.44 (RStudio, Inc. GNU Afferro General Public License v3, Boston, MA, 2016) with the graphical user interface (GUI) rBiostatistics.com (rBiostatistics.com, London, UK, 2017).

Monitoring

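### The named univariable tests treat patients clustered by surgeon and centre as independent, and the plan gives no method for clustering in the risk-factor analysis

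*Combined protocol and SAP*

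**What the plan says.** Study data in the combined protocol and SAP describes the data as surgeon-based and adds: "The data will indicate in an anonymized fashion that surgeons belong to a specific centre". Data collection methods states that "all consecutive patients undergoing liver resections by one individual surgeon over three months are included". The Summary sets no minimum number of patients per centre, so clusters may be very unequal in size.

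Statistical methods names these tests: "Continuous variables will be compared with the Student t test, the Mann-Whitney U test and the Kruskal-Wallis H test or one-way ANOVA as appropriate", and "Differences among proportions derived from categorical data will be compared using the Fisher test and the Pearson chi-square". Their use goes beyond description: "Univariate analysis will be performed to test factors associated with post-operative complications and 90-day mortality", with two-sided p < 0.05 as the threshold. The model is then given as: "Multivariable regression models will be used to identify factors independently associated with these outcomes and to adjust for differences in confounders", reported as adjusted odds ratios with 95% confidence intervals.

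No section mentions clustering, intraclass correlation, mixed models, GEE, robust standard errors, or surgeon or centre as a stratum or covariate. Statistical methods lists no covariates. The variables that Data collection methods gives as examples (comorbidities, procedure type) are patient-level.

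**The concern.** Patients of the same surgeon or centre share technique, selection and aftercare, so their outcomes are likely to be correlated. The Introduction itself gives a reason to expect this, stating that "patient selection and both centre and surgeon experience are all cited factors which may influence outcomes following major liver surgery". Tests that assume independence then overstate the information on any factor that varies between surgeons or centres.

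Identifying independent risk factors is the stated secondary objective (Outcomes). The p-values most affected would be those for surgeon- or centre-level factors such as experience or volume. Patient-level factors whose frequency differs between surgeons, such as procedure type, would be affected less. If the regression were run as ordinary logistic regression, its confidence intervals would be too narrow in the same pattern. The result would be too many factors declared as risks, more so for complications than for mortality.

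**Working it through.** **Inputs from the documents.** At least 2000 patients and 2.5% 90-day mortality (Sample size), so 2000 × 0.025 = 50 expected deaths; two-sided 5% tests (Statistical methods). There is no power calculation to reproduce.

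**Assumed, because not given.** 5 to 40 patients per surgeon; between-surgeon SD on the logit scale 0.3 to 1.0; complication rate 35%.

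**Formula check.** For a factor constant within a cluster of size m, the design effect is DE = 1 + (m − 1) × ICC, and the true type I error of an unadjusted 5% test is 2 × (1 − Φ(1.96/√DE)).

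- m = 20, ICC 0.02: DE = 1 + 19 × 0.02 = 1.38; type I error 9.5%. Simulation at 2.5% mortality gave 9.4%.
- m = 20, ICC 0.05: DE = 1.95; type I error 16.0%. Simulation gave 15.7%.
- Over m = 5 to 40 and ICC 0.005 to 0.05, the formula gives 5.2% to 25.4%.

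**Chi-square test as named.** 10,000 simulated datasets per setting, N = 2000, equal series, no true effect. The assumed SDs correspond to ICCs of 0.002–0.034 for mortality and 0.020–0.165 for complications. Type I error for a surgeon-level factor, over SD 0.3 to 1.0:

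| Patients per surgeon | Mortality | Complications |
|---|---|---|
| 5 | 4.9–6.7% | 5.9–12.9% |
| 10 | 5.1–8.5% | 7.4–21.5% |
| 20 | 5.9–12.4% | 9.7–33.8% |
| 40 | 5.9–18.9% | 13.7–47.6% |

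A patient-level factor whose frequency varies between surgeons (assumed logit SD 1.0) gives 4.8–7.1% for mortality and 5.5–17.6% for complications. An evenly spread factor gives 4.6–5.4% for both. The Monte Carlo standard error at 5% is 0.2 percentage points.

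**If ordinary logistic regression were used** (the plan does not say). 2,000 datasets per setting, surgeons nested in centres (1 to 4 per centre), unequal series, the same SDs as the total split equally between the two levels, two prognostic patient covariates. Type I error over all settings:

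| Factor | Mortality | Complications |
|---|---|---|
| Evenly spread | 4.2–5.8% | 4.1–5.7% |
| Patient-level, varying between surgeons | 4.3–8.5% | 5.2–23.7% |
| Surgeon-level | 4.2–22.7% | 6.5–53.7% |
| Centre-level | 4.8–30.2% | 9.1–64.8% |

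With 10 or fewer patients per surgeon, the mortality ranges are 4.3–5.9% (patient-level, varying) and 4.2–10.8% (surgeon-level).

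**Candidate remedies in the same regressions, all factors:**

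| Standard errors | Mortality | Complications |
|---|---|---|
| Robust by surgeon only (worst, centre-level factor) | up to 14.0% | up to 15.7% |
| Robust by centre, simple correction | 4.2–10.1% | 4.0–9.2% |
| Robust by centre, Mancl-DeRouen variance, t reference | 3.6–6.3% | 3.4–6.1% |

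The Monte Carlo standard error here is 0.5 points at 5%. A smaller repeat with 400 datasets per setting gave about 3.5–8% for the last row, and up to about 20% for surgeon-only clustering.

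**Sparse groups.** At 2.5% mortality the chance of no deaths is 0.975^20 = 60%, 0.975^40 = 36% and 0.975^100 = 8% for groups of 20, 40 and 100.

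**The case against.** The strongest reply is that the definite fault lies in the less important step. The independent risk factors come from the multivariable models, and adjusted odds ratios are compatible with a mixed model, GEE or robust errors; nothing commits the study to a naive regression. The objective is secondary. The largest error rates belong to surgeon- or centre-level factors, which the plan never lists for testing, and they need 40 resections per surgeon in three months, SD 1.0 and, at 2000 patients, about 20 centres. That sits uneasily with worldwide recruitment, and 2000 is a minimum. Between-surgeon variation explained by case mix was not discounted. The choice between GEE and a mixed model is partly preference.

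Much of this stands as a limit on size. The regression is an omission rather than an error, the upper figures are extremes, and mortality with small series is little affected. It does not remove the point. The univariable tests are named, are applied to both outcomes at p < 0.05, and ignore the sampling structure. Adjusting for confounders does not deal with correlated observations. Nor does the concern rest only on cluster-level factors: a patient-level factor that varies between surgeons reaches 17.6% for complications in the chi-square simulation.

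**Conclusion.** The concern holds and should be fixed. It is firm that the named tests assume independence, that the sampling is by surgeon within centre, and that no section says how this is handled. The size is conditional, because series length, between-surgeon variation and the complication rate are assumptions. Within the assumed ranges, inflation is negligible for evenly spread factors, modest for mortality with 10 or fewer patients per surgeon (at most 8.5% for a surgeon-level factor under the chi-square test), and material for complications, where a surgeon-level factor exceeds the nominal 5% in every setting examined (5.9% to 47.6%).

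**What to change.** In Statistical methods, state that:

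- Risk-factor inference for both 90-day mortality and complications uses logistic regression with cluster-robust standard errors or GEE, clustered by centre. This also covers surgeons nested in centres.
- A small-sample variance correction (for example Mancl-DeRouen) with a t reference is applied. It matters most if centres are few or very unequal.
- The univariable risk-factor tests use the same approach with one covariate. Fisher's test stays as a descriptive fallback, labelled as unadjusted for clustering, where cells are too sparse for a model.
- Any 95% confidence interval for overall 90-day mortality is cluster-robust.
- A mixed model with random intercepts for surgeon within centre is a sensitivity analysis and the source of any reported between-cluster variance.

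If length of stay or the Comprehensive Complication Index is formally compared, name a centre-clustered counterpart for those outcomes too.

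Confirm that the export carries anonymised identifiers for both surgeon and centre. Study data allows one participant to enter a colleague's cases under their own login, so the login alone may not identify the surgeon.

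The cost is one paragraph, slightly more analysis work and that check. The intervals will widen. In the simulations, mortality intervals were 1.02–1.64 times as wide for a surgeon-level factor (1.02–1.20 with 10 or fewer patients per surgeon), 1.02–1.18 times for a patient-level factor varying between surgeons, and 1.01–1.08 times for an evenly spread factor. The change does not by itself remove confounding by centre.

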The *primary objectives* of LiverGroup.org is to develop a non-proprietary international data set on the **morbidity** and **mortality** following liver resections among international surgeons. Morbidity will be recorded according to the Clavien-Dindo Classification of Surgical Complications, the FABIB Liver Surgery-Specific Classification and the novel Comprehensive Complication Index® (CCI®). Mortality will be captured until the 90th postoperative day.

The *secondary objective* is to identify independent risk factors for morbidity and mortality using multivariable regression models.

Participant timeline and study duration

The enrolment period will last 3 months and a minimum of 3 months period is required for follow-up of each patient. Surgeons may start enrolment at any time within the 12-month enrolment time frame: 1st of January 2019 until the 31st of December 2019. The Management Committee may decide to prolong the patient enrolment if deemed necessary.

Sample size

The study aims for the maximum number of patients it will be able to recruit and has no power calculation for specific outcomes. Assuming a 2.5% 90-day mortality rate, at least 2000 patients will have to be recruited to be able to perform a meaningful multivariate analysis on independent risk factors postoperative mortality

Recruitment

Surgeons joining LiverGroup.org are encouraged to propose a country or regional leader (north/south etc). This process will be guided by the management committee. The responsibilities of the *Regional* and *Country Leaders* representing each country in the world include, among others to recruit and co-ordinate collaborators in their own country or region as well as to provide additional scientific and administrative support to their collaborators. Additionally, personal contacts of the LiverGroup.org team will be used to recruit centres. Furthermore, the members of the Management Committee are seeking for endorsement of the International Hepato-Pancreato-Biliary Association (IHPBA), European-African Hepato-Pancreato-Biliary Association (E-AHPBA), the American Hepato-Pancreato-Biliary Association (AHPBA), and the Asian-Pacific Hepato-Pancreato-Biliary Association (A-PHPBA).

Data collection, management, and analysis

Study data

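### Youden cut-offs taken from the study's only dataset are planned without an interval or optimism correction, and the coding of continuous variables in the models is not stated

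*Combined protocol and SAP*

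**What the plan says.** All references are to the Combined protocol and SAP.

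- **Statistical methods, cut-offs.** One sentence covers them: ROC curves are to be drawn and Youden's "index will be used to identify ideal cut-off points for continuous variables". It names no variable and no outcome, and mentions no interval, resampling or held-out data.
- **Statistical methods, tests.** "Continuous variables will be compared with the Student t test, the Mann-Whitney U test and the Kruskal-Wallis H test or one-way ANOVA", as appropriate. Fisher and chi-square tests are listed separately, for proportions from categorical data.
- **Statistical methods, models.** "Results of the multivariable analyses will be reported as adjusted odds ratios (OR) with 95% confidence intervals". How continuous variables enter these models is not stated. On significance: "All p values will be 2-sided and considered statistically significant if" p is below 0.05.
- **Outcomes.** The secondary objective "is to identify independent risk factors for morbidity and mortality using multivariable regression models".
- **Sample size.** There is no power calculation. At an assumed 2.5% 90-day mortality, 2000 patients is given as the minimum for the multivariable analysis.
- **Data collection methods.** The validation described is a data audit, in which a peer is to "perform a validation of the number of and date of deaths". It does not validate cut-offs or models.

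**The concern.** The Youden cut is the value that maximises sensitivity plus specificity in the sample at hand. Its performance in that same sample is therefore too good on average, and when events are few its location varies widely between samples. The plan calls such cuts ideal and provides nothing that would show a reader either effect.

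The Introduction hopes the data will help surgeons and patients judge which level of complexity to offer. A threshold for, say, a standardised liver remnant or a laboratory value (our examples; the plan names none) could be published with no sign of how far it would move in new data.

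A second, conditional problem comes from the unstated coding. If the cut variable were tested or modelled in the data that chose it, nominal p-values and confidence intervals would no longer mean what they say.

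**Working it through.** **Inputs from the plan.** Minimum 2000 patients and 2.5% mortality (Sample size); two-sided 0.05 (Statistical methods). Expected deaths: 2000 x 0.025 = 50, leaving 1950 survivors. The plan gives no formula behind 2000, so that figure can be neither reproduced nor refuted.

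**Assumptions (ours).** One predictor, normal with SD 1 in both groups, mean 0 in survivors and m in deaths. Then m = ln(OR per SD). Patients are treated as independent. Odds ratios of 1.3 and 2.0 per SD stand for a weak and a strong predictor.

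**Formulas.** Youden index at cut c: J(c) = sensitivity + specificity - 1. Under the model its true value is J(c) = Phi(c) - Phi(c - m), which is largest at c = m/2, where J = 2 Phi(m/2) - 1.

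- OR 1.3: m = 0.262, best possible J = 2 Phi(0.131) - 1 = 0.10.
- OR 2.0: m = 0.693, best possible J = 2 Phi(0.347) - 1 = 0.27.

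**Step 1: harm whatever the use.** Simulated samples of 50 deaths and 1950 survivors, with the cut chosen in each sample and the direction of effect set in advance:

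| True OR per SD | 5th-95th percentile of chosen cut | Apparent J (mean) | True J at chosen cut (mean) | Optimism |
|---|---|---|---|---|
| 1.3 | about -0.7 to +1.1 SD | 0.17 | 0.09 | 0.08 |
| 2.0 | about -0.2 to +1.0 SD | 0.32 | 0.26 | 0.06 |

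On the survivors' scale, -0.7 to +1.1 SD runs from about the 24th to the 86th percentile, and -0.2 to +1.0 SD from about the 42nd to the 84th. A commoner outcome helps: at an assumed 30% event rate among 2000 patients and OR 1.3, the range narrows to about -0.5 to +0.6 SD.

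**Step 2: only if the cut variable is tested in the same data.** Null predictor, 50 deaths, unadjusted chi-square at nominal 0.05:

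- Direction fixed in advance: p < 0.05 in about a quarter of samples (24 to 27% across simulation set-ups). A fixed direction is plausible for the liver remnant, given the Introduction's "thus highlighting the importance of future liver remnant percentage (FLR) which has since been repeatedly demonstrated".
- Direction free: about 41 to 44%.
- If a t test on the continuous variable must be passed first: 2.8% (fixed) and 5.0% (free), so there is no inflation.

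**Step 3: only if an odds ratio is reported at the cut in the same data.** 50 deaths, OR 1.3 per SD, logistic model with one assumed confounder (OR 1.5 per SD, correlation 0.3), direction fixed: mean estimate 2.26 against a true 1.51, with 84% coverage for the nominal 95% interval. The mean standard error (0.34) is not below the SD of the error (0.31), so the loss comes from the upward shift and not from too narrow an interval.

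**Step 4: the alternative.** In the same adjusted setting, a continuous term gives 1.30 per SD against a true 1.30, with 95% coverage.

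**The case against.** A reader might infer that the plan will test and model its own cut-offs, so that 25 to 44% of null continuous factors would be declared significant and the reported adjusted odds ratios inflated. The documents do not support that. The tests listed for continuous variables are tests of continuous variables, with chi-square and Fisher reserved for categorical data. The cut-off sentence follows the modelling sentences and is not linked to them. On the plain reading the cuts are descriptive. If continuous variables are also modelled as continuous, the adjusted odds ratios are unaffected. What stands on the other side is that the coding in the models is never stated, so the worse use is not excluded.

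It is also fair to say that a weak predictor exaggerates the instability, since few analysts would publish a threshold for one. At OR 2.0 the range is about 1.2 SD wide instead of 1.8 SD. That narrows the problem without removing it, and the optimism in J falls only from 0.08 to 0.06.

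Finally, this is an observational audit without a power calculation, 2000 is a minimum, and complications will be commoner than deaths. More events reduce both the instability and the optimism. They do not supply the missing interval, and risk factors are a stated objective.

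**Conclusion.** The point holds in a limited form. Following the plan as written yields cut-offs whose location is imprecise and whose apparent performance is overstated, with nothing planned to show either. At about 50 deaths the 5th to 95th percentile range is some 1.2 to 1.8 SD wide and the Youden index is overstated by about 0.06 to 0.08, for true odds ratios of 2.0 down to 1.3 per SD. These sizes rest on one normal predictor, independent patients and the plan's minimum sample; they illustrate and do not forecast.

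The false-positive and odds-ratio figures in steps 2 and 3 are conditional on a use the plan does not state and should not be quoted as properties of the planned analysis. The point bears on the secondary objective and on any published thresholds, not on the 90-day mortality estimate. The change is worth making because it is cheap.

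**What to change.** Replace the cut-off sentence in Statistical methods with text such as:

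> Continuous predictors enter the univariate tests and multivariable models as continuous terms (linear, or a spline where the number of events allows), with adjusted odds ratios per stated increment. Youden-derived cut-offs are not used in tests or models. Any Youden cut-off is labelled exploratory and reported with a bootstrap interval for the cut and optimism-corrected sensitivity, specificity and Youden index, resampling by surgeon or centre.

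Resampling by surgeon or centre follows from the Study data section, which makes the data surgeon-based and records the centre each surgeon belongs to. The cost is a few sentences and a small bootstrap, with no extra data. The downside is that there is no longer a single in-sample threshold to quote as ideal.

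### Risk factors for complications and 90-day mortality would be declared by an unadjusted p<0.05 rule, with no limit on candidates and no exploratory label

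*Combined protocol and SAP*

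**What the plan says.** The Outcomes section gives the secondary objective as to "identify independent risk factors for morbidity and mortality using multivariable regression models".

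The Statistical methods section sets out two steps. First: "Univariate analysis will be performed to test factors associated with post-operative complications and 90-day mortality". Second: "Multivariable regression models will be used to identify factors independently associated with these outcomes and to adjust for differences in confounders". Results are to be reported as adjusted ORs with 95% confidence intervals. One threshold covers everything: "All p values will be 2-sided and considered statistically significant if" p is below 0.05. The section also plans ROC curves and Youden's index to choose cut-offs for continuous variables.

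The Sample size section says there is no power calculation for specific outcomes and that recruitment is as large as can be achieved. It then gives a floor tied to this analysis: "Assuming a 2.5% 90-day mortality rate", "at least 2000 patients will have to be recruited to be able to perform a meaningful multivariate analysis".

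No section lists the candidate factors, limits their number, says how factors enter the model, adjusts for multiple testing, plans shrinkage or internal validation, or calls the results exploratory. The case report form is on the study website and was not available for this review.

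**The concern.** A p<0.05 rule applied to an open list of candidates does two things. It lets through about one in twenty of the factors that have no effect. When events are few, it also keeps mainly those estimates of real factors that happened to come out large. If the factors that pass are reported as independent risk factors with ordinary ORs and intervals, the reader cannot tell chance findings from real ones, and the ORs of weak real factors are too high.

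The list of risk factors is the study's stated secondary objective, and the mortality model is the only justification given for the 2000-patient floor. The Introduction hopes that the study's data as a whole will help surgeons and patients judge what level of complexity to offer. A factor list read as established would feed into that.

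**Working it through.** **Inputs from the plan.** Two-sided threshold 0.05 (Statistical methods); minimum 2000 patients and 2.5% mortality (Sample size).

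**Inputs assumed.** 20, 30 or 40 candidate factors, 5 of them real; independent binary factors, each present in 30% of patients; true OR 1.5, 2 or 3. The plan gives none of these.

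**1. Deaths at the plan's minimum.** 2000 × 0.025 = 50. The 2000 itself cannot be derived from the plan. It would follow from ten deaths per parameter and five parameters (5 × 10 / 0.025 = 2000), but that is an inference.

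**2. Expected false factors.** Roughly 0.05 × number of null candidates. With 15, 25 or 35 null candidates: 0.75, 1.25, 1.75. Neither patients nor deaths enter this formula. If all candidates were null, the chance of at least one false factor would be 1 − 0.95^m: 64% for m = 20, 79% for 30, 87% for 40.

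**3. Simulation at 2000 patients** (250 datasets per row; univariate p<0.05, then multivariable p<0.05; mortality only). Share false = false / (false + true).

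| Candidates | True OR | False declared | True declared (of 5) | Share false | Mean OR of declared true factors |
|---|---|---|---|---|---|
| 20 | 1.5 | 0.63 | 1.36 | 32% | 2.09 |
| 30 | 1.5 | 1.09 | 1.37 | 44% | 2.13 |
| 40 | 1.5 | 1.49 | 1.34 | 53% | 2.14 |
| 20 | 2 | 0.58 | 3.28 | 15% | 2.35 |
| 30 | 2 | 1.06 | 3.15 | 25% | 2.37 |
| 40 | 2 | 1.36 | 3.16 | 30% | 2.41 |
| 30 | 3 | 1.01 | 4.72 | 18% | 3.24 |

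With 25 candidates, separate runs gave 12% false at OR 3, and a true OR of 1.5 declared at about 2.2.

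**4. Why a true OR of 1.5 is exaggerated.** With 30% prevalence and OR 1.5, mortality is 2.18% in 1400 unexposed patients (30.5 deaths) and 3.24% in 600 exposed (19.4 deaths). The standard error of the log OR is √(1/30.5 + 1/1369.5 + 1/19.4 + 1/580.6) = 0.294. Significance needs a log OR above 1.96 × 0.294 = 0.577, that is, an estimate above 1.78. An estimate close to the true 1.5 cannot pass. Power is about 28%.

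**5. Four times the patients.** 8000 × 0.025 = 200 deaths. The standard error halves to 0.147 and the smallest significant OR falls to exp(1.96 × 0.147) = 1.33. In simulation (30 candidates, 100 datasets) a true OR of 1.5 is declared at 1.59 and a true OR of 2 at 2.00. False factors remain: 1.18 (24% of those declared) and 1.03 (17%). Over 25-30 candidates the range is about 0.6-1.2.

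**6. Does it depend on univariate screening?** The plan does not state that univariate p-values decide entry. A full model with 25 candidates, read at p<0.05, gives 0.9 false factors and a true OR of 1.5 declared at 2.2. The result is much the same.

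**7. Alternatives at 50 deaths, true OR 1.5.**
- Bonferroni over 30 factors (0.05 / 30 = 0.00167): power falls from 28-30% to about 4%, and factors that pass are reported at about 2.8.
- 5% false-discovery control (25 candidates): false factors fall to 0.05, but true factors declared fall from 1.3 to 0.3 of 5. Nothing is declared in 71-79% of datasets, and declared true ORs average about 2.8 before shrinkage.
- Reporting every pre-specified factor: the mean OR over all true-factor estimates is 1.50, so the selection bias is gone. Shrinkage cuts the root-mean-square error of the log OR over all coefficients from 0.38 to 0.17. Much of that gain comes from the null factors.

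**8. Not counted above.** A null continuous variable cut at its Youden optimum and tested in the same data was significant in about 42% of runs. This matters only if the cut variables are then tested, which the plan does not say.

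**The case against.** The study is an observational audit with no treatment hypothesis, and unadjusted p-values for a secondary, descriptive aim are common. The number of candidates is not in the documents, and 50 deaths is a floor, since recruitment is open-ended. Some real effects may be large: the Introduction cites 12% mortality for ALPPS, which against the assumed 2.5% is a crude OR of (0.12/0.88) / (0.025/0.975) = 5.3. At such sizes exaggeration is slight.

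All of this stands, and it limits the point. Several stronger readings are tempting, and the documents do not support them:

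- A reader might infer that many, or most, declared factors will be false. The expected number is about one, and a majority appears only with about 40 candidates and weak effects.
- A reader might blame the false factors on the small number of deaths. Few deaths cause low power and exaggeration. The false-positive count depends on the threshold and the number of null factors.
- A reader might extend the point to every outcome. The p<0.05 rule covers all tests, but factor analyses are named only for complications and 90-day mortality.
- A reader might take univariate screening as planned. The text gives no entry rule, and the aim of adjusting for confounders does not require one.

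What the objection does not answer is that the plan intends to name factors as independently associated with outcome, on significance alone, without saying that the list is exploratory.

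**Conclusion.** The point holds in a limited form. One unadjusted threshold decides which factors are named, candidates are not limited, and nothing marks the result as exploratory. At the planned minimum, and assuming 20-40 independent candidates with 5 real ones, about 0.6-1.5 false mortality factors would be declared per analysis. The false share ranges from about half (40 candidates, OR 1.5) down to 12-18% (25-30 candidates, OR 3). Exaggeration is material at OR 1.5, moderate at OR 2 (about 2.4), and small at OR 3 or with about 200 deaths.

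A reader might also conclude that formal multiplicity control is the answer. At about 50 deaths it is not: it would declare almost nothing and would worsen exaggeration among what it does declare. The change is worth making, but the primary endpoint, 90-day mortality as a rate, is not affected.

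**What to change.** Replace the significance rule for the factor analyses in Statistical methods with wording such as:

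> For each outcome, candidate factors are fixed on clinical grounds before data export, with their number limited by the number of events. Univariate results are descriptive and do not decide entry. All pre-specified factors stay in the model and are reported with adjusted ORs and 95% CIs whatever their p-value, with penalised or bootstrap-shrunken estimates alongside. Factors with p<0.05 are described as exploratory associations, not as established independent risk factors.

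The limit matters because keeping all of 25 candidates at the minimum size would leave 50 / 25 = 2 deaths per parameter. Do not add false-discovery control as a condition for reporting a factor.

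The cost is plan wording, a little more analysis work in R, and no new data. The conclusion will be more cautious, and the shrunken estimates will lie closer to the null.
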